# Table 3. Exploratory Endpoints Modeling Details

In addition, figures will be generated for the following endpoints.

# **Table 4. Figures for Exploratory Endpoints**

Exploratory Endpoints	Figure Descriptions			
CCI				
% CBL in fasting plasma PCSK9 at Day	Box and whisker plot of individual % CBL versus treatment will be presented and overlaid			
Page 19				
CCI				

	I
42	with arithmetic means.
% CBL in Triglycerides, Total cholesterol, HDL-C, direct LDL-C, Total cholesterol/HDL-C ratio, and non HDL- C at Baseline and all post-Baseline time points	Line plot of LSMs with 90% CIs for all treatment groups including the placebo group with time on X-axis. Four (4) lines corresponding to the 4 treatment groups will be overlaid on the same plot.
% CBL in AST, ALT, ALP, GGT at Baseline and all post-Baseline time points	Line plot of LSMs with 90% CIs for all treatment groups including the placebo group with time on X-axis. Four (4) lines corresponding to the 4 treatment groups will be overlaid on the same plot.
CCI	

• Pharmacogenomic and biomarker data:

Pharmacogenomic and biomarker data will be collected and retained for future analyses, but will not be analyzed for the purposes of CSR.

## 6.4. Subset Analyses

For the primary endpoint subset analysis by the whole liver PDFF stratification categories provided below may be considered.

- Screening liver fat  $\geq 8\%$  and < 15%;
- Screening liver fat  $\geq 15\%$ .

# If any site enrolls 50% or more of the total number of subjects in the study site-specific analysis may be conducted.

#### 6.5. Baseline and Other Summaries and Analyses

CCL

A breakdown of demographic data will be provided for age, race, weight, height and body mass index. Each of these will be summarized by sex at birth and treatment in accordance with the sponsor reporting standards. In addition, the demographic data will be summarized by treatment only in accordance with the sponsor reporting standards. Baseline summary of fasting glucose, triglycerides, HDL-C, waist circumference, AST, ALT, alkaline phosphatase, GGT and whole liver PDFF will be presented for each treatment group and overall. Baseline summary of stratification factors, namely, diabetes status (presence or absence) and MRI-PDFF categories ( $\geq 8\%$  and <15% or  $\geq 15\%$ ) will be provided. The number and proportion of subjects enrolled in each study site will also be presented.

Summary tables will show end of study subject disposition and will show which subjects were analyzed for pharmacodynamic (FAS) CCI as well as for safety (AEs and laboratory data). Frequency counts will be supplied for subject discontinuation(s) by treatment. Data will be reported in accordance with the sponsor reporting standards.

#### 6.6. Safety Summaries and Analyses

A set of summary tables split by treatment will be produced to evaluate any potential risk associated with the safety and toleration of the study treatments.

The standard safety endpoints detailed in Section 3.5 will be listed and summarized in accordance with sponsor reporting standards, where the resulting data presentations will consist of subjects from the safety analysis sets. The analyses of non-standard safety data will also utilize safety analysis set and the methods are described below.

Any untoward findings identified on physical examinations conducted during the active collection period will be captured as AEs, if those findings meet the definition of an AE. Data collected at screening that are used for inclusion/exclusion criteria, such as laboratory data, ECGs, and vital signs, will be considered source data, and will not be required to be reported, unless otherwise noted.

# **Adverse Events**

Adverse events will be summarized by treatment and in accordance with current Pfizer data standards. The AEs will be sorted alphabetically within a system organ class. Summary tables will be provided for treatment-emergent adverse events (TEAEs) and AEs occurring prior to randomization will only be listed.

# Laboratory Data

All planned, quantitative, standard safety laboratory data presented in Table 7 of the protocol and non-standard safety laboratory data that are not reported independently will be listed and summarized in accordance with the sponsor reporting standards as applicable. Baseline is as defined in Section 3.5.2.

# Vital Signs

Absolute values and changes from Baseline in seated systolic and diastolic blood pressure and pulse rate will be summarized by treatment and study day, according to sponsor reporting standards. Tables will be paged by parameter. Baseline is as defined in Section 3.5.3.

Mean changes from Baseline for systolic and diastolic blood pressure and pulse rate will be plotted against study day. On each plot there will be one line for each treatment, with all treatments on the same plot, including the placebo.

For Baseline subtracted seated systolic and diastolic blood pressure and pulse rate, the differences between each dose and placebo (dose – placebo) will be summarized (N, mean, 90% CI) and plotted (mean, 90% CI) for each dose and day including follow-up.

Maximum absolute values and maximum changes from Baseline for vital signs, over all measurements taken post-dose after randomization will also be tabulated by treatment using categories as defined in the Appendix. Numbers and percentages of subjects meeting the categorical criteria will be provided. All planned and unplanned post-dose time points will be counted in these categorical summaries. All values meeting the criteria of potential clinical concern will be listed.

Maximum decrease and increase from Baseline for seated systolic and diastolic blood pressures, and maximum increase from Baseline for seated pulse rate will be summarized by treatment, according to sponsor reporting standards.

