Upon single dose administration, the only TEAE reported by more than 1 subject was upper respiratory tract infection (1 subject while on placebo and 2 subjects while receiving 100 mg). Furthermore, with repeated dosing, the only TEAE reported by more than 2 subjects exposed to PF-05221304, across the entire dose range evaluated, was headache. All TEAEs were self-limiting requiring isolated use of concomitant medications and/or non-drug treatments to manage them.

Across the other safety-related data collected, drug-related, laboratory parameter changes were observed although none were remarkable following single dose administration of PF-05221304. Upon repeated dose administration of PF-05221304, identified adverse drug reactions (ADRs) included elevation in blood triglycerides and reduction of platelet count. This included a gradual increase in fasting and post-prandial serum triglycerides with repeated doses \geq 40 mg/day with effect plateauing over the 14-day dosing period. At steady-state, the increase in mean fasting serum triglycerides (placebo-adjusted change from baseline) ranged from 35%-50% at doses \geq 40 mg/day; while increases in weighted-mean $(AUC_{24}/24)$ serum triglycerides (placebo-adjusted change from baseline) ranged from 20%-60%, at these same doses. At the doses \geq 60 mg/day, a gradual decrease in platelet count was observed with repeated doses over the 14 day dosing period. This observation was not noted at PF-05221304 doses up to 40 mg/day and no signs or symptoms of platelet dysfunction were apparent based on the safety assessments performed. These ADRs have not been observed with administration of single oral doses as high as 240 mg. There were no apparent abnormalities noted in the other safety-related assessments such as blood pressure and cardiac conduction intervals [assessed on 12-lead electrocardiograms (ECGs)].

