# 2.1. Study Objectives

The study objectives are shown below along with their corresponding endpoints.

Primary Objective(s):	Primary Endpoint(s):
To determine the effect of co-administration of PF-05221304 and PF-06865571 on whole liver fat compared to placebo, PF-05221304 administered alone, and PF-06865571 administered alone in subjects with non- alcohlic fatty liver disease (NAFLD).	Relative change from Baseline in whole liver fat at Day 42, as assessed by magnetic resonance imaging proton density fat fraction (MRI-PDFF).
Secondary Objective(s):	Secondary Endpoint(s):
To evaluate safety and tolerability of PF- 05221304 and PF-06865571 co-administration compared to placebo, PF-05221304 administered alone, and PF-06865571 administered alone in subjects with NAFLD.	Assessment of treatment-emergent adverse events (and serious adverse events), clinical laboratory tests including lipids, vital signs, and 12-lead electrocardiograms (ECGs).

Tertiary/Exploratory Objective(s):	Tertiary/Exploratory Endpoint(s):
To evaluate the effect of co-administration of PF-05221304 and PF-06865571, on liver function tests (LFTs) compared to placebo, PF- 05221304 administered alone, and PF- 06865571 administered alone in subjects with NAFLD.	
 
Percent change from Baseline at all time points for:
 
Alanine aminotransferase (ALT), Aspartate aminotransferase (AST).
 
Alkaline Phosphatase.
 
Gamma-glutamyl transferase (GGT).
 

To evaluate effects of co-administration of PF- 05221304 and PF-06865571 on lipids compared to placebo, PF-05221304 administered alone, and PF-06865571 administered alone in subjects with NAFLD.	
 
Percent change from Baseline at all time points for:
 
Triglycerides.
 
Total cholesterol, HDL-C, direct LDL-C, Total cholesterol/HDL-C ratio, and non- HDL-C.
 

CCI	
To evaluate the PD effects of co-administration of PF-05221304 and PF-06865571 compared to placebo, PF-05221304 administered alone, and PF-06865571 administered alone, in adults with NAFLD.	Analyses for PD parameters: % Change from Baseline to Day 42 in Apolipoproteins (A1, B100 and C3). % Change from Baseline to Day 42 in plasma proprotein convertase subtilisin/kexin type 9 (PCSK9)
Pa	ge 6

CCI

CCI		

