## Electrocardiogram

Absolute values and changes from Baseline in QT, heart rate, QTcF, QTc, PR, and QRS will be summarized by treatment and day using sponsor reporting standards. Tables will be paged by parameter. Baseline is as defined in Section 3.5.4.

Mean changes from Baseline in QT, heart rate and QTcF will be plotted against study day. On each plot there will be one line for each treatment, with all treatments on the same plot including the placebo.

In addition for Baseline subtracted QT, heart rate and QTcF, the differences between each dose and placebo (dose – placebo) will be summarized (N, mean, 90% CI) and plotted (mean, 90% CI) for each dose and day including follow-up.

ECG endpoints and changes from Baseline (QTcF, PR and QRS) will also be summarized descriptively by treatment using categories as defined in the Appendix (for QTc these correspond to ICH E14). Numbers and percentages of subjects meeting the categorical criteria will be provided. All planned and unplanned postdose timepoints will be counted in these categorical summaries. All values meeting the criteria of potential clinical concern will be listed.

Maximum absolute value (post-dose after randomization) and the maximum increase from Baseline for QTcF, PR and QRS will be summarized by treatment according to sponsor reporting standards.

Listings of subjects with any single post-dose value >500 msec will also be produced for QTcF.

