# Non-standard Safety Analysis

## Serum Creatinine, Serum Cystatin C and Associated eGFRs

Absolute values and changes from Baseline in Scr, serum cystatin C, eGFRs obtained from Scr and cystatin C will be summarized by treatment and day. Mean absolute values of all four parameters will be plotted separately against study day. On each plot there will be one line for each treatment, all treatments on the same plot including the placebo. Mean changes from Baseline in eGFRs will also be plotted against study day.

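### The secondary objective compares the combination's safety with placebo and each monotherapy, but SAP 6.6 plans vital-sign and ECG differences against placebo only and none for platelets

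*SAP*

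**What the plan says.** - **Objective.** SAP 2.1 (and Protocol 2) state the secondary objective as the safety and tolerability of the combination "compared to placebo, PF-05221304 administered alone, and PF-06865571 administered alone in subjects with NAFLD". Its endpoints are adverse events, laboratory tests including lipids, vital signs and ECGs. Protocol 1.6.3 repeats the aim of characterising safety for co-administration against each drug on its own.
- **Vital signs.** For baseline-subtracted blood pressure and pulse rate, SAP 6.6 plans that "the differences between each dose and placebo (dose – placebo) will be summarized (N, mean, 90% CI") and plots them by day, including follow-up.
- **ECG.** The same form is used: "In addition for Baseline subtracted QT, heart rate and QTcF, the differences between each dose and placebo (dose – placebo) will be summarized".
- **Laboratory data.** Planned quantitative results from Protocol Table 7, which lists platelet count, "will be listed and summarized in accordance with the sponsor reporting standards as applicable". No between-arm difference is specified.
- **Renal markers.** Under Non-standard Safety Analysis, "eGFRs obtained from Scr and cystatin C will be summarized by treatment and day", again with no difference.
- **Platelets.** Protocol 1.3.2 reports that with repeated PF-05221304 dosing "identified adverse drug reactions (ADRs) included elevation in blood triglycerides and reduction of platelet count". Protocol 3.2 gives platelets their own individual withdrawal threshold. Protocol 1.5.1 gives the effect of DGAT2 inhibition on PF-05221304 platelet lowering as one reason for choosing monkeys for the combination toxicity study.
- **Lipids and liver tests.** SAP 6.3 plans MMRM estimates with 90% CIs for all five treatment comparisons, including the combination against each monotherapy.

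**The concern.** In a factorial trial of a combination, the contrast that shows what the second drug adds to the safety profile is combination minus monotherapy. The objective asks for that contrast, and SAP 6.6 does not plan it for blood pressure, pulse rate, QT, heart rate or QTcF. It plans only the contrast with the smallest arm.

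The two identified reactions of PF-05221304 are also handled differently. Triglycerides get a model, five contrasts, a figure and an interim predictive probability against PF-05221304 alone. Platelet count is not named in the readable SAP text and gets by-arm summaries only.

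At stake is whether the report carries pre-planned estimates, with uncertainty, for two of the three comparators in its own secondary objective. If not, readers will make those comparisons by eye, or choose contrasts after seeing the data.

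**Working it through.** **Planned differences set against the objective**

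| Measure | Against placebo | Combination against each monotherapy |
|---|---|---|
| BP, pulse rate | difference, 90% CI | none planned |
| QT, heart rate, QTcF | difference, 90% CI | none planned |
| Platelet count | none planned | none planned |
| Triglycerides, other lipids, liver tests | difference, 90% CI | difference, 90% CI |

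The SAP's phrase about each dose is read here as each active arm, since the trial has one dose level per drug.

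**Arm sizes (Protocol 3.1 and 9.1).** With 98 randomized 1:2:2:2, placebo has 98 × 1/7 = 14 and each active arm 98 × 2/7 = 28. Completers are 12 and 24, and 84/(1 − 0.14) = 97.7, or 98. The documents size only the primary endpoint, and the stated power of more than 90% is reproduced:
- |ln 0.70| = 0.357
- SE = 0.32 × √(1/12 + 1/24) = 0.113
- 0.357/0.113 − 1.645 = 1.51, giving 93.4%

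This confirms the arm sizes; nothing in the safety point depends on it.

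**Precision in SD units, assuming equal SD across arms.** SE = SD × √(1/n₁ + 1/n₂); 90% half-width = 1.645 × SE.

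| Contrast | SE | 90% half-width |
|---|---|---|
| Active − placebo, 28 vs 14 | √(1/28 + 1/14) = 0.327 | 0.54 |
| Combination − monotherapy, 28 vs 28 | √(2/28) = 0.267 | 0.44 |
| Active − placebo, 24 vs 12 | √(1/24 + 1/12) = 0.354 | 0.58 |
| Combination − monotherapy, 24 vs 24 | √(2/24) = 0.289 | 0.47 |

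The ratio is 0.267/0.327 = 0.816, so the omitted contrasts have an SE about 18% smaller. The documents give no SD for platelets, BP or QTcF, so the results stay in SD units.

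**Can the contrast be rebuilt from the placebo differences?** Subtracting two of them gives the right point estimate. Their intervals share the placebo arm, though. Treating them as independent gives, for completers, 1.645 × √(2 × (1/24 + 1/12)) = 0.82 SD instead of 0.47 SD, which is 1.73 times too wide.

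**How many intervals the fix adds**
- Vital signs and ECG: 6 parameters (systolic BP, diastolic BP, pulse rate, QT, heart rate, QTcF) × 2 contrasts × 5 post-baseline visits (Days 5, 14, 28, 42 and follow-up) = 60.
- Platelets: 5 contrasts × 4 or 5 visits = 20 to 25.
- With no true effects, 10% of 90% intervals exclude zero: about 6 of the 60, and 2 to 2.5 of the platelet intervals.

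**The case against.** The strongest reply is that the information is already there. SAP 5.2 commits to sample size, mean and SD for continuous endpoints, and SAP 6.6 summarises all four arms by day and plots vital signs, QT, heart rate and QTcF with all arms together. Anyone can form an unadjusted combination-minus-monotherapy difference and interval from those tables, without going through the placebo differences. This stands. A reader might infer that the trial cannot estimate these contrasts, or reports nothing except the comparison with placebo; the by-arm summaries rule that out.

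Protocol 9.7 calls for descriptive safety summaries and rules out formal inference for vital signs and ECG. An objective to evaluate safety can be met by side-by-side tables, and no document requires more. That limits the fix to estimation. It does not exclude the fix, because the SAP already reports 90% CIs against placebo, and the added intervals are of the same kind.

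On platelets, several facts lower the expected effect. The fall was seen at 60 mg/day and above and not noted up to 40 mg/day, while this trial gives 15 mg twice daily, or 30 mg/day. PF-06865571 did not lower platelets in the monkey or clinical studies. Co-administration did not alter PF-05221304 toxicity in monkeys, and PF-05221304 AUC was about 19% lower with the combination. A reader might infer that a further fall with the combination is expected; nothing in the documents supports that or gives it a size. Even so, the reassuring human dose-range data come from up to 14 days in healthy adults, and this trial doses subjects with NAFLD for up to 42 days.

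Platelets are also not neglected. They are summarised through Table 7, assessed for abnormality, covered by an individual threshold and included in the monthly blinded laboratory review. Triglycerides have a reason for fuller treatment: they are a named exploratory endpoint, and Protocol 1.6.3 asks whether PF-06865571 mitigates their rise.

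**Conclusion.** The mismatch is real and modest. SAP 6.6 does not plan the combination-minus-monotherapy estimates for vital signs and ECG that the secondary objective implies, and it plans no between-arm difference for platelet count. The trial will hold the data; the gap is in what is pre-planned and presented. Under equal SDs, the omitted contrasts would have standard errors about 18% smaller than those reported. That figure follows from the allocation alone and does not show harm.

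The point does not extend to all safety measures, because triglycerides, other lipids and liver tests already have all five comparisons. Nor does it support adding platelets to the interim analysis: SAP 7 leaves the standard interim safety content to an IRC charter, which is not among the documents. The conclusion on platelets also assumes that the sponsor reporting standards, likewise not available, do not already require a difference.

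This is a cheap improvement. The primary analysis and the sample size are untouched.

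**What to change.** By SAP amendment before database release:

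1. In SAP 6.6, Vital Signs and Electrocardiogram, add combination minus PF-05221304 and combination minus PF-06865571 (N, mean, 90% CI, same days) to the existing difference tables and plots.
2. Under Non-standard Safety Analysis, using the Safety Analysis Set, add platelet count with the MMRM form already specified for lipids: log relative change as response, log baseline as covariate, and the five treatment contrasts with 90% CIs. Report no tests or p-values.
3. State that all these intervals are descriptive and unadjusted for multiplicity.

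No extra subjects, visits or samples are needed, and existing programs can be reused. The cost is about 60 more vital-sign and ECG intervals and 20 to 25 platelet intervals. Some will exclude zero by chance, so the report should say in advance that isolated exclusions are not to be read as signals.

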## Electrocardiogram

Absolute values and changes from Baseline in QT, heart rate, QTcF, QTc, PR, and QRS will be summarized by treatment and day using sponsor reporting standards. Tables will be paged by parameter. Baseline is as defined in Section 3.5.4.

Mean changes from Baseline in QT, heart rate and QTcF will be plotted against study day. On each plot there will be one line for each treatment, with all treatments on the same plot including the placebo.

In addition for Baseline subtracted QT, heart rate and QTcF, the differences between each dose and placebo (dose – placebo) will be summarized (N, mean, 90% CI) and plotted (mean, 90% CI) for each dose and day including follow-up.

ECG endpoints and changes from Baseline (QTcF, PR and QRS) will also be summarized descriptively by treatment using categories as defined in the Appendix (for QTc these correspond to ICH E14). Numbers and percentages of subjects meeting the categorical criteria will be provided. All planned and unplanned postdose timepoints will be counted in these categorical summaries. All values meeting the criteria of potential clinical concern will be listed.

Maximum absolute value (post-dose after randomization) and the maximum increase from Baseline for QTcF, PR and QRS will be summarized by treatment according to sponsor reporting standards.

Listings of subjects with any single post-dose value >500 msec will also be produced for QTcF.

# Non-standard Safety Analysis

## Serum Creatinine, Serum Cystatin C and Associated eGFRs

Absolute values and changes from Baseline in Scr, serum cystatin C, eGFRs obtained from Scr and cystatin C will be summarized by treatment and day. Mean absolute values of all four parameters will be plotted separately against study day. On each plot there will be one line for each treatment, all treatments on the same plot including the placebo. Mean changes from Baseline in eGFRs will also be plotted against study day.

## 7. INTERIM ANALYSES

If, after randomization of approximately 50% subjects of planned number of subjects, a monthly safety review reveals that the study meets one or more criteria listed in Protocol Section 3.3, an interim analysis will be performed in an un-blinded manner by a prespecified IRC, independent from study team.

Before any interim analysis is initiated, the details of the objectives, decision criteria, dissemination plan, and method of maintaining the study blind as per Pfizer's SOPs will be documented and approved in an IRC charter. The analysis details will be documented and approved in an interim analysis SAP or final SAP.

An IA will be conducted after approximately 50% of randomized subjects reach their Week 6 visit (ie, Visit 10 in Schedule of Activities) or drop out of the study before that visit.

The analysis sets for the IA are:

- 1. Safety Analysis Set: All randomized and treated subjects
- 2. Efficacy/PD Analysis Set: All randomized and treated subjects who completed their Week 6 visit (ie, Visit 10 in Schedule of ActivityActivityActivities) or discontinued the study.

For whole liver PDFF, triglycerides (and total cholesterol, HDL-C, direct LDL-C, Total cholesterol/HDL-C ratio, and non HDL-C, AST, ALT, ALP, GGT), the descriptive summarization and inferential statistical analysis (ANCOVA or MMRM) as indicated in Section 6 will be performed using the Efficacy/PD Analysis Set. Standard safety data as described in the IRC Charter will be summarized using the Safety Analysis Set. The figures related to these descriptive and inferential analyses will be using the "Efficacy/PD Analysis Set".

For whole liver PDFF and triglycerides, additional analysis related to predictive probability will be conducted. The Bayesian predictive probability that the following decision critera will be met at the end of the study given the interim data will be calculated using Pfizer internal validated software. The IRC Statistician will utilize the IA outputs (from ANCOVA analysis for whole liver PDFF and MMRM analysis for triglycerides) to compute the predictive probabilities, and will then provide the probability values to the unblinded programmer to be included in the IA table outputs.

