## Mixed Model for Repeated Measurements (MMRM)

This model will be used for the analysis of endpoints with more than one post-Baseline collection time point. All observed data collected during the post-Baseline treatment period will be utilized. The MMRM analysis will be performed with treatment, study day and treatment-by-study day interaction as fixed effects, Baseline value of the analysis endpoint, and Baseline whole liver PDFF. If the endpoint being analyzed is log-tranformed, the Baseline value of the analysis endpoint and the Baseline whole liver PDFF will also be log-transformed. Repeated measures model with unstructured correlation matrix will be utilized. If this does not converge then compound symmetry structure will be considered. Additionally, the number of covariates may be reduced to improve model fit. Estimates of

treatment effects will be assessed using least square means (LSMs) and CIs at each time point. LSM difference for each comparison along with the CIs and 2-sided p-values will be provided. If there are major deviations from the statistical assumptions underlying this model then alternative transformations (eg, log) or non-parametric analyses may be presented. Justification for any alternative to the planned analysis will be given in the study report.

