## 5.3. Methods to Manage Missing Data

In case of continuous endpoints, all available data will be utilized in the MMRM. The MMRM will provide unbiased estimates in case of missing at random (MAR). For the analysis of safety endpoints, the sponsor data standard rules for imputation will be applied. In case of biomarkers if the concentrations are above the upper limits of quantification such values will be truncated at the upper limit of quantification in all summary tables. If the concentrations are below the lower limits of quantification (LLQ) such values will be imputed by 0.5\*LLQ. However, in listings they will appear as reported.

	Page 15	
CCI		

In all pharmacokinetic data presentations (except listings), concentrations below the limit of quantification (BLQ) will be set to zero. (In listings BLQ values will be reported as "<LLQ", where "LLQ" will be replaced with the value for the LLQ.)

In summary tables and plots of the median values at each time point, statistics will be calculated having set concentrations to missing if one of the following cases is true:

- 1. A concentration has been collected as ND (ie, not done) or NS (ie, no sample),
- 2. A deviation in sampling time is of sufficient concern or a concentration has been flagged anomalous by the pharmacokineticist.

Note that summary statistics will not be presented at a particular time point if more than 50% of the data are missing.

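### The interim Efficacy/PD set admits recent enrollees to the lipid and liver-enzyme models only if they drop out; the main cost is some precision

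*SAP*

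**What the plan says.** SAP Section 7 sets the timing of the interim analysis: "An IA will be conducted after approximately 50% of randomized subjects reach their Week 6 visit" or drop out before it. It then defines two sets. The first is "Safety Analysis Set: All randomized and treated subjects", used for standard safety summaries. The second, the Efficacy/PD set, is "All randomized and treated subjects who completed their Week 6 visit" "or discontinued the study". Nothing limits the second set by date of randomisation.

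The models for whole liver PDFF, lipids and liver enzymes "as indicated in Section 6 will be performed using the Efficacy/PD Analysis Set". The two predictive probabilities take their inputs "from ANCOVA analysis for whole liver PDFF and MMRM analysis for triglycerides". S-C1 asks for 95% confidence, at study end, that the Day 42 triglyceride change is lower on the combination than on PF-05221304 alone.

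On the MMRM itself, SAP Section 5.2 says "All observed data collected during the post-Baseline treatment period will be utilized", and Section 5.3 adds "The MMRM will provide unbiased estimates in case of missing at random (MAR"). At study end, Section 6.3 analyses these endpoints on the full analysis set.

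**The concern.** The protocol's Schedule of Activities places Visit 10 on Day 39 to 42. A subject randomised more recently than that before the cut cannot have completed Week 6, so discontinuation is the only way into the Efficacy/PD set. Subjects from the same weeks who are still on treatment are excluded from the MMRM, although fasting lipids and liver enzymes are scheduled at Days 5, 14 and 28.

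This has two consequences. First, data already collected are not used, at an interim with about 14 subjects per active arm. Second, the missing-at-random argument covers a cohort with incomplete follow-up; it does not cover a sample in which recent entrants are kept because they dropped out and removed because they did not. If dropout relates to triglycerides and does so unequally by arm, the interim triglyceride contrast shifts.

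That contrast feeds the S-C1 predictive probability, one of the two that the SAP specifies. SAP Section 5.1 allows interim results to inform internal planning or a futility stop.

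**Working it through.** **Inputs from the documents.** 98 randomised 1:2:2:2, about 14% dropout, at least 84 completers (protocol 9.1); interim at about 50%, read here as 49 of 98 (SAP 7); 28 per active arm at study end (SAP 9.2). Check of the plan's figures: 84 / (1 − 0.14) = 97.7, rounded up to 98. The documents give no figure for the dropout share of the interim set.

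**Assumptions, not in the documents.** Constant accrual of r subjects per week; dropout spread evenly over 6 weeks; log-triglyceride SD 0.35 with between-visit correlation 0.6; a true combination-minus-PF-05221304 difference of −0.20 log units.

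**Dropout share of the set.** Of the 6r subjects randomised in the last 6 weeks, on average half of the eventual 14% have already left:

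- recent dropouts = 6r × 0.14 / 2
- older cohort = 49 − recent dropouts
- share = (0.14 × older cohort + recent dropouts) / 49
- on-treatment subjects left out = 6r − recent dropouts

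For r = 4, recent dropouts = 24 × 0.07 = 1.68, the older cohort = 47.32, and the share = (6.62 + 1.68) / 49 = 16.9%.

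| r per week | Recent dropouts | Dropout share | On-treatment left out |
|---|---|---|---|
| 2 | 0.84 | 15.5% | 11.2 |
| 3 | 1.26 | 16.2% | 16.7 |
| 4 | 1.68 | 16.9% | 22.3 |
| 6 | 2.52 | 18.4% | 33.5 |
| 8 | 3.36 | 19.9% | 44.6 |

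The enrichment is about 1 to 3 subjects over four arms.

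**Effect on the triglyceride contrast.** A simulation (3000 runs per setting; visits at Days 5, 14, 28 and 42; unstructured covariance; treatment by visit; cut at the 49th subject to complete or drop out) compared the SAP set with all treated subjects and all their observed data. A third set, subjects randomised at least 42 days before the cut, served as a reference free of selection. The predictive probability (PP) used the SAP 9.2 formula, with the number having a Day 42 value as the interim n.

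| Dropout | r | Bias, SAP set | Bias, all observed | SD, SAP set | SD, all observed | PP of S-C1: SAP / date cohort / all observed |
|---|---|---|---|---|---|---|
| Random | 3 | −0.0035 | −0.0044 | 0.142 | 0.135 | 0.609 / 0.609 / 0.615 |
| Random | 5 | +0.0006 | +0.0012 | 0.138 | 0.131 | 0.599 / 0.600 / 0.601 |
| Random | 8 | −0.0003 | −0.0024 | 0.143 | 0.131 | 0.598 / 0.598 / 0.608 |
| Triglyceride-driven, PF-05221304 arm | 3 | −0.0039 | +0.0012 | 0.143 | 0.134 | 0.611 / 0.600 / 0.603 |
| Triglyceride-driven, PF-05221304 arm | 5 | −0.0065 | −0.0003 | 0.138 | 0.128 | 0.615 / 0.599 / 0.608 |
| Triglyceride-driven, PF-05221304 arm | 8 | −0.0124 | −0.0001 | 0.141 | 0.127 | 0.629 / 0.602 / 0.609 |

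Simulation error on each bias is about 0.14 / √3000 = 0.0026. The random-dropout values are therefore indistinguishable from zero, and the value of −0.0039 at 3 per week is only about 1.5 simulation errors. With triglyceride-driven dropout in every arm, the bias in the SAP set was −0.002 to −0.007.

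- Precision: SD about 0.14 against 0.13; 1 − (0.13 / 0.14)² = 14% lower variance when all observed data are used.
- Predictive probability, PF-05221304-driven case, against the date cohort: 0.611 − 0.600, 0.615 − 0.599 and 0.629 − 0.602, so 1.1 to 2.7 points too high. Against all observed data the excess is 0.7 to 2.0 points.

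**The case against.** Several stronger readings are tempting, and the documents do not support them.

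- **That data from subjects still on treatment are discarded altogether.** They are not. These subjects are in the interim Safety set; they are missing only from the Efficacy/PD models.
- **That the set contradicts the SAP's MMRM rule.** Section 5.2 describes which visits the model uses for subjects in the analysis set; it does not define the set. A restricted interim set and use of all visits within it are compatible. The narrower point stands: the set is still selected on dropout.
- **That S-C1 is materially flattered.** This needs common, triglyceride-driven withdrawal that is more frequent on PF-05221304. Protocol 1.3.2 links the triglyceride rise to 40 mg/day or more, and this study gives 15 mg twice daily, or 30 mg/day. Section 1.6.3 does allow that increases may occur at high lipogenesis inhibition. Entry excludes values above 400 mg/dL, and Section 3.2 lists a consistent rise to 800 mg/dL or more as an example for permanent withdrawal. A subject at the entry cap would have to double: ln 2 = 0.69, about two of the assumed SDs of 0.35. Such withdrawals may be few.
- **That the PDFF analysis has the same fault.** It has a single post-baseline scan. Subjects still on treatment have none, and early terminators are scanned only after at least 4 weeks of dosing.

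It is also fair to say that the interim is not tied to a formal error rate, and that the IRC charter, which may set its own data-cut rule, is not among the documents. What remains is a real selection on dropout with an avoidable loss of precision.

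**Conclusion.** The point holds as a minor one. As written, the set brings recent enrollees into the interim lipid and liver-enzyme MMRMs only through dropout. The certain cost is precision, with about 14% of the variance of the Day 42 triglyceride contrast avoidable. Bias is undetectable under random dropout. In the unfavourable case tried it is at most about 0.012 log units against an SD of 0.14.

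These sizes rest on the assumed accrual rate, triglyceride SD, correlation, true difference and dropout models. Faster accrual raises the dropout share and the number of subjects left out. S-C1 is an end-of-study criterion, so only its interim predictive probability is touched. The final analyses, the PDFF ANCOVA and E-C1 are essentially unaffected.

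**What to change.** In SAP Section 7 and the IRC charter:

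- Run the interim MMRMs (lipids, ALT, AST, ALP, GGT) on all randomised and treated subjects, using all post-baseline data observed by the cut. Day 42 values not yet due are then missing because of calendar time, which suits the missing-at-random assumption.
- State that the interim n entered in the Section 9.2 code is the number with an observed Day 42 value. The code does not say, and counting subjects without one would overstate the interim information.
- Leave the PDFF ANCOVA set as it is, with all available Day 42 scans. A rule requiring 42 days since randomisation would drop recent subjects who completed Visit 10 early in its Day 39 to 42 window and have a valid scan, for no gain.

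The cost is a few sentences and slightly more interim data cleaning, for the 11 to 45 on-treatment subjects under the accrual rates assumed. No new data are needed.
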